15.5	Site Initiation	49
15.6	Monitoring	50
15.7	Required Reports	50
16	STUDY REQUIREMENTS	52
16.1	Quality Assurance	52
16.2	Monitoring	53
17	PROCEDURES AND INSTRUCTIONS	55
17.1	Special safety-related procedures	55
17.2	Administrative procedures	55
17.3	Ethics and Good Clinical Practice	55
APPEND	DIX A - STUDY SCHEDULE	56
APPEND	DIX B- Supplemental TRANSPLANTATION /OTHER APPENDICES	58
APPEND	DIX C – Supplemental TRANSPLANTATION	59
REFEREI	NCE LIST	60

CONFIDENTIAL	Clinical Protocol	DATE	Р	age
		9Dec2019		T
	mented Disc Regeneration in the Treatment of the or without Intervertebral Disc Herniation –	WRITER TG, DB, PW	NO. 9	REV 6

STUDY CONTACTS

Sponsor: Vivex Biologics, Inc.

[name]

[contact]

Medical Monitor: H. [name]

Chief Medical Officer Vivex Biologics, Inc.

[contact]

Clinical Representative: [name]

Clinical Program Manager

Vivex Biologics, Inc.

[contact]

Principal Investigator: [name]

[name]

[name]

[name] [contact]

CONFIDENTIAL	Clinical Protocol	DATE 9Dec2019	P	age
	mented Disc Regeneration in the T reatment of the or without Intervertebral Disc Herniation –	WRITER TG, DB, PW	NO. 10	REV 6

PROTOCOL SYNOPSIS

Title	Viable Allograft Supplemented Disc Regeneration in the Treatment of Patients with Low Back Pain with or without Intervertebral Disc Herniation – VAST Trial
Objective	To evaluate the safety and efficacy of viable allograft transplantation for the treatment of patients with symptomatic disc degeneration and tissue loss
Study Design	Multi-center, prospective, parallel, triple arm study to assess patients who participated in the VAST trial and receiving either viable allograft, saline, or allograft after cross-over. These patients will be evaluated at baseline, injection, 6 months, and 12 months. Subjects will then have an option for a 24 months and 36 months extension after their index procedures. Patients who received saline or active allograft in the VAST study, will be allowed to receive viable allograft and followed for an additional 12 and 24 months after that election. These subjects will need to meet initial inclusion/exclusion criteria again before another injection.

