Endpoints	 Primary: Improvement in Oswestry Disability Index (ODI) at 6 and 12 months after treatment. Durability of Oswestry Disability Index (ODI) at 24 and 36 months after initial inclusion compared with 12 month improvement. Improvement in Visual Analogue Scale of Pain Intensity (VASPI) at 6, and 12 months after treatment. Durability of Improvement in Visual Analogue Scale of Pain Intensity (VASPI) 24 months and and 36 months after initial inclusion compared with 12 month improvement.
	Secondary Page 10 of 62

CONFIDENTIAL	Clinical Protocol	DATE	P	age
		9Dec2019		
	mented Disc Regeneration in the $\underline{\mathbf{T}}$ reatment of th or without Intervertebral Disc Herniation –	WRITER TG, DB, PW	NO. 11	REV 6

	 Improvement in ODI, SF-36, and VASPI at 6 and 12 months after treatment Improvement in ODI, SF-36, and VASPI scores for optional 24 month and 36 month follow up subjects X-ray and MRI measurements at 6 and 12 months after treatment AE/SAE rates after treatment Hospitalization rate at 12, 24, or 36 months after treatment Re-operation rate at 12, 24, or 36 months after treatment Resource utilization following treatment and at 6 and 12 months (and optional 24 & 36 month) follow up visits 		
Study Population	Patients evaluated for degenerative intervertebral disc disease demonstrating Pfirrmann Grade [3-6] by MRI		
Clinical Sites	Up to twenty (20) sites in the United States		
Sample size and	Approximately 220 subjects randomized to viable allograft or placebo or control in 3.5:1:1 ratio:		
randomization	$n_{active} = 140$ $n_{placebo} = 40$ $n_{control} = 40$		
	For study extension: The original randomized population will be pooled and reconsented for an optional follow up for 24 and 36 months.		
Study Design	The study is composed of three separate phases. There will be the Screening Phase followed by the Active Phase equaling 12 months then followed by the optional long term follow up at 24 months and 36 months. Patients need to meet entry criteria for all phases.		

CONFIDENTIAL	Clinical Protocol	DATE 9Dec2019	Р	age
	mented Disc Regeneration in the T reatment of the or without Intervertebral Disc Herniation –	WRITER TG, DB, PW	NO. 12	REV 6

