3 OBJECTIVE

The objective of this study is to evaluate the safety and efficacy of viable allograft transplantation for the treatment of patients with symptomatic disc degeneration and tissue loss.

The primary criterion is the outcome of the Oswestry Low Back Pain Disability Questionnaire (OPDQ) modified according to Hudson-Cook and calculated as the Oswestry Disability Index (ODI) at 6 and 12 months after transplant, and the Visual Analogue Scale of Pain Intensity (VASPI) at 6, and 12 months following allograft supplementation. Secondary parameters of efficacy will include SF-36. Structural outcomes will be assessed using X-ray and Magnetic Resonance Image (MRI) measurements at 12 months. Safety will be assessed by the incidence and severity of adverse events (AEs) and clinically important changes in laboratory tests. All subjects (excluding conservative care crossover subjects) will be randomized to include MRI at 6-month follow-up (MRI or no MRI, ratio 1:1) in addition to all other assessments. Subjects randomized to conservative care will be assessed at 3 months. If at 3 months these subjects demonstrate a significant decline in condition, they will be offered the option to receive allograft treatment and will be followed for the subsequent 6 and 12 months. The conservative care subjects that crossover to the allograft treatment group will all receive an MRI at 6-month and 12-month follow-up after allograft treatment.

A correlation of the clinical results (scores) and the morphological results (X-ray, MRI) will be evaluated. All additional efficacy and safety data will be analyzed descriptively.

The optional long-term follow up will allow for additional objectives to be analyzed. At 24 and 36 months, subjects will have the opportunity to fill out VASPI, ODI, SF-36, and Resource Utilization forms which will be analyzed and compared to the original 12-month data. The active allograft and placebo cross over to allograft treatment at 24 months will also be asked to fill out the same questionnaires. This data will be compared to the first 12 months of data in the placebo group.

CONFIDENTIAL	Clinical Protocol	DATE 9Dec2019	P	age
	mented Disc Regeneration in the T reatment of th or without Intervertebral Disc Herniation –	WRITER TG, DB, PW	NO. 18	REV 6

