6.3 Blinding

The assignment to treatment (active allograft, or placebo, or conservative care) is open label at Day 0 of the Active Phase to the extent that subjects receiving allograft or placebo will not be aware of what they have received, while those assigned to conservative care will be aware. All site study staff will be aware of the group to which each subject is randomized. Sites will be trained to ensure that subjects receiving the allograft or placebo treatment will remain blinded to their treatment throughout the study duration. Subjects will be unblinded during the study exit or upon signing of the new informed consent for the study extension.

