6.4 Treatments administered

Subjects screened and eligible for the Active Phase of the study will have diagnosis of the affected disc to normal standard procedures for all treatment groups. At the baseline visit (Day 0) of the Active Phase, eligible subjects who are randomized into allograft or placebo treatment will undergo a transplantation procedure. This procedure will consist of the following:

- 1. Transplant supplemental viable allograft into the affected disc
- 2. Transplant placebo saline treatment as alternative arm of study.

These procedures are outlined in detail in Appendices B and C respectively.

At 24-months, placebo saline subjects and active allograft subjects are eligible to receive the allograft injection.

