CONFIDENTIAL	Clinical Protocol	DATE	Р	age
		9Dec2019		T
TITLE: V iable A llograft S upplemented Disc Regeneration in the T reatment of		WRITER TG, DB, PW	NO.	REV
Patients with Low Back Pain with VAST-001-017	th or without Intervertebral Disc Herniation –	. 0, 22,	31	6

7.1.6 Active Phase Month 12 (+ 30 days) or VA5:

All randomized subjects will return to the clinic 12 months (+ 30 days) subsequent to transplantation for safety and efficacy assessments as outlined in Appendix A. ODI, VASPI, and SF-36 questionnaires will be completed by the subject, with assistance from physician or physician designee. All subjects will receive an MRI and X-ray at the 12-month follow-up visit. A review of resource utilization through the 12 Month visit will be completed.

7.1.7 Optional Long-Term Follow Up Month 24 & Month 36 (+ 3 Months) or VA6 & VA7:

All randomized subjects will have an option to continue to be monitored for long-term follow up. Before study procedures begin, the informed consent addendum 2 for study extension will need to be signed. At the 24-month in-office visit, subjects will first be reevaluated for inclusion/exclusion and fill out VASPI, ODI, SF-36, and Resource Utilization. If eligible for allograft treatment, the PI will perform a neurological exam, physical exam, labs, and give the subject applicable questionnaires. All randomized subjects will have the option to receive allograft treatment at 24 months in accordance with the inclusion/exclusion re-evaluation. An MRI and x-ray will be performed on subjects receiving another injection for safety purposes. If needed, a second office visit may be scheduled within 14 days of the original evaluation to allow appropriate time for the laboratory investigation and MRI. All follow up subjects will complete VASPI, ODI, SF-36, and Resource Utilization questionnaires at both follow up visits. The 36-month will consist of questionnaires and can be performed over the phone if the subject chooses.

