8 INCLUSION / EXCLUSION CRITERIA

8.1 Inclusion Criteria

Patients will be entered into this study only if they meet ALL of the following criteria:

- Able to provide an English written Informed Consent
- Age 18 to 60 years inclusive
- Male or female
- Body mass index <35
- Pfirrmann Grade [3-6]
- Radiographic confirmation by MRI/X-ray of:
 - (1) translational instability defined as ≤5 mm, or
 - (2) angular instability defined as ≤5°
- Back pain (with or without radicular leg pain) measured by:
 - (3) ODI of at least 40%, and
 - (4) VASPI of at least 40mm
- Pathologic level between L1 and S1
- 1 or 2 vertebral level involvement that has been evaluated for at least 6 months and treated with conservative care
- Symptomatic back pain attributable to intervertebral disc for a minimum of 6 months
- No previous surgical treatment at the disc level(s) being considered
- Psychosocially, mentally and physically able to fully comply with this protocol, and follow-up schedule
- Ability to undergo allograft transplantation
- Life expectancy >2 years
- No contraindications to MRI
- No history of malignancy (basal cell carcinoma) or chronic infectious disease (e.g. HIV, Hepatitis)
- Agree to use appropriate contraception; not planning on becoming pregnant for 24 months after treatment
- Patient disc for transplant confirmed by inter-discal pressure measurement, or disc-imaging study.
- No signs or symptoms of infection
- No chronic use (>7 consecutive days) of anticoagulants (such as aspirin) or NSAIDs prior to treatment

CONFIDENTIAL	Clinical Protocol	DATE	P	age
		9Dec2019		
	mented Disc Regeneration in the $\underline{\mathbf{T}}$ reatment of th or without Intervertebral Disc Herniation –	WRITER TG, DB, PW	NO. 34	REV 6

8.2 Exclusion criteria:

- Seropositive or seronegative spondyloarthropathy
- Type III Modic changes
- Prior surgeries of segments between L1 and S1
- Chemonucleolysis or percutaneous laserectomy of the affected disc prior to the study
- Chronic facet syndrome
- Stenosis of the spinal canal that is moderate to severe or more in degree
- Spondylodiscitis
- Spondylolisthesis (lysis and degenerative)
- Severe motor deficit or cauda equina disorder based on investigator determination
- Congenital abnormalities of the spinal nerves
- Pelvic and inguinal angiopathy
- Neurogenic inguinal syndrome
- Syringomyelia
- Diastenomatomyelia
- Traumatic neurological disorders
- Diseases of the kidney (nephritis, pyelonephritis)

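### Protocol section 3 sets unblinded, self-selected patients injected at 24 months against the placebo arm's first 12 months, a contrast that is not randomised, concurrent or independent

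*Protocol*

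**What the plan says.** Protocol section 3 (Objective) introduces the optional long-term follow-up and then states: "The active allograft and placebo cross over to allograft treatment at 24 months will also be asked to fill out the same questionnaires". The next sentence names the comparator: "This data will be compared to the first 12 months of data in the placebo group".

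Other sections settle who is on the injected side:

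- **Arms.** Section 6.4: "At 24-months, placebo saline subjects and active allograft subjects are eligible to receive the allograft injection".
- **Choice.** Section 7.1.7: "All randomized subjects will have the option to receive allograft treatment at 24 months in accordance with the inclusion/exclusion re-evaluation". The extension has no new randomisation and no concurrent control. The synopsis says: "The original randomized population will be pooled and reconsented for an optional follow up for 24 and 36 months".
- **Requalification.** The synopsis (Study Design) says: "These subjects will need to meet initial inclusion/exclusion criteria again before another injection". Section 8.1 sets the severity thresholds as "ODI of at least 40%, and" a VASPI of 40 mm or more.
- **Blinding.** Section 6.3: "Subjects will be unblinded during the study exit or upon signing of the new informed consent for the study extension". Section 7.1.7 has the extension consent signed before any extension procedure, so patients know their original arm, and that they are getting allograft, before the 24-month injection.

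No section gives a baseline, a pairing rule or a test for this comparison. SAP section 5.2 places the final analyses after the last 12-month visit, and the SAP does not mention the extension. Its preface cites a protocol issued on 11 May 2018; the current protocol is dated 9 December 2019.

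**The concern.** The sentence creates an allograft-versus-placebo contrast outside the randomised comparison. Both outcomes, ODI and VASPI, are self-reported. On one side patients know they have received allograft; on the other they were kept unaware that they had received saline. The injected patients are selected by their own choice and by their scores at 24 months. The calendar period differs, some patients have a second allograft injection rather than a first, and some supply data to both sides.

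A difference found this way mixes any treatment effect with expectation, selection, time, repeat exposure and dependence between the groups. What is at stake is any efficacy statement drawn from the extension.

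**Working it through.** **1. Inputs.** The plan states no figure for this comparison, so there is none to reproduce. From the documents: arm sizes 140 / 40 / 40 (SAP section 4); SD 15.5 ODI points, reliability 0.75 to 0.91 and a clinically relevant difference of 9 points (Protocol section 13.3); windows of ±3 months at months 24 and 36, and +30 days at month 12 (Appendix A). Section 13.3's measurement error does reproduce: 15.5 × √(1 − 0.75) = 7.75.

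**2. Overlap.** The injected side can hold up to 140 + 40 = 180 patients. Up to 40 of these are placebo crossovers, who could be the whole comparator group.

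**3. Timing.** An injection at the 24-month visit falls between months 21 and 27, and the month-36 questionnaire between months 33 and 39. The interval is therefore 33 − 27 = 6 to 39 − 21 = 18 months, against 12 months (+30 days) for placebo. The month-36 score may be taken by telephone.

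**4. Selection and baseline (assumed model).** True ODI is normal with mean 35, 45 or 55 and SD 15.5 × √reliability; error SD is 15.5 × √(1 − reliability). Patients enter if the observed baseline is at least 40. Response to each treatment has mean 0 or 10 and SD 10, and the 24-month injection is no better than saline. Patients are injected if the observed month-24 ODI is again at least 40. Expectation effects, VASPI and opt-in behaviour are left out. Each scenario starts from 1,000,000 draws. Improvement is positive, and the difference is injected minus placebo. The extremes over all scenarios are:

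| Baseline for injected side | Mean / reliability / response | Placebo, first 12 months | Injected, to month 36 | Difference |
|---|---|---|---|---|
| Month 24 | 35 / 0.75 / 0 | 3.90 | 2.17 | −1.73 |
| Month 24 | 55 / 0.75 / 10 | 11.17 | 11.81 | +0.64 |
| Original | 35 / 0.75 / 0 | 3.90 | −0.76 | −4.66 |
| Original | 55 / 0.91 / 10 | 10.42 | 17.03 | +6.61 |

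The true difference is zero throughout. Part of the +6.61 arises because change from the original baseline counts two treatment responses on the injected side. The largest value is 6.61 / 9 = 73% of the difference the protocol calls clinically relevant.

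**5. Dependence (hypothetical, since no test is planned).** If only c placebo crossovers are injected (n1 = c, n2 = 40) and their two changes have correlation ρ, the variance of the difference is proportional to 1/n1 + 1/n2 − 2ρc/(n1 × n2). A test that ignores the last term has true type I error 2 × [1 − Φ(1.96 / SE ratio)], where the SE ratio is true over assumed. For c = 40:

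- ρ = +0.5: variance 0.050 − 0.025 = 0.025, SE ratio 0.707, type I error 0.0056.
- ρ = −0.5: variance 0.050 + 0.025 = 0.075, SE ratio 1.225, type I error 0.1095.

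Over c = 10 to 40 and ρ from −0.5 to +0.5, a nominal 5% test would run at about 0.6% to 11%. Dependence can make it too strict as well as too lenient.

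**The case against.** The strongest reply is that this is one loosely worded exploratory sentence. Section 3 says that additional data are analysed descriptively, section 13.2.2 makes secondary variables exploratory, and SAP sections 7.5 and 9.1 rest trial success on the randomised 12-month co-primary endpoints alone. That stands, with a limit. The descriptive statement comes before the extension paragraph, so its reach to the extension is an inference, and a descriptive contrast carries the same bias as a tested one. The synopsis does list 24- and 36-month durability under primary endpoints, but against 12-month improvement, not against placebo.

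A reader might infer four stronger points that the documents do not support:

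- **A known false-positive rate.** If unblinding alone shifted scores by 3 to 5 points, a normal approximation to the rank test (SD 15.5, independent groups) would give 11% to 21% with 20 injected against 40 placebo, and 15% to 32% with 50 against 40. The shifts and injected numbers are invented, no test or alpha is planned, and the groups are not independent.
- **Bias that always favours allograft.** Unblinding would tend that way, but selection can act in either direction.
- **Re-injected patients as failures of the first injection.** Meeting the thresholds again shows only that a patient is symptomatic at 24 months. Someone who improved from a much higher score, or who responded and relapsed, can requalify.
- **Nothing worth keeping.** For placebo crossovers, comparing the year after allograft with their own year on saline is a usable within-patient contrast, though open-label and with allograft always second.

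**Conclusion.** The concern holds as a fault in one planned exploratory comparison. The injected patients are unblinded, opt in, requalify on severity, mix first and repeat injections, and include patients who also form the comparator. No section corrects for any of this or defines a baseline.

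The overlap limit (40 of 40 placebo patients) and the 6-to-18-month interval follow from the documents. The size of the bias cannot be fixed from them. In the assumed model it runs from −1.7 to +0.6 ODI points or from −4.7 to +6.6, depending on the baseline, before any expectation effect. These ranges rest on the assumed means, responses and normal distributions and are illustrations only.

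A reader might go on to doubt the trial's placebo-controlled result. The documents give no ground for that here: the randomised 12-month comparison does not use these data.

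**What to change.** Replace the comparison sentence in Protocol section 3 with text to this effect:

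- For patients injected at 24 months, report the change from the pre-injection 24-month score to month 36 as uncontrolled and descriptive, with a confidence interval, separately for former placebo and former allograft patients.
- Limit any comparison with the first 12 months on saline to placebo crossovers. Analyse it within patient (paired) and label it open-label and order-confounded.
- Draw no between-group inference against the placebo arm from the extension. The placebo-controlled claim rests on the randomised 12-month comparison.

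The report should add that the uncontrolled change includes regression to the mean, because the pre-injection score had to pass a threshold. In the model above with zero mean response it is 0.33 to 2.17 ODI points.

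Two related conflicts must be reconciled so that the reporting groups and time points are clear. Section 6.4 names the placebo and allograft arms for the 24-month injection, while sections 6.9 and 7.1.7 speak of all randomised subjects. The synopsis describes follow-up at 12 and 24 months after the later injection, while Appendix A ends at month 36.

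The cost is a small text change and the loss of an exploratory between-group claim. No data are lost.

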4 BACKGROUND

Degenerative changes of the lumbar segments are an inevitable consequence of the aging and are often a reason for chronic back pain and neurological complications. It has been estimated that nearly 80% of the population suffer from lower back pain at least once during their lifetime^{2,3} and during recent years degenerative changes of the lumbar segments have become an outstanding medical problem in the industrialized nations.^{4,5} Progress in clinical medicine has acknowledged several patho-mechanisms of intradiscal mass change(s) with respect to disc herniation as well as degeneration. In general, the main reason for disc herniation is attributed to trauma, and the degree of degeneration of the disc and the trauma causing herniation vary widely but are correlated. Making the connection important but perhaps more challenging is information regarding degenerative changes linked to genetic, metabolic, and mechanical imbalance. ^{6,7,8,9,10}

The development of chronic back pain after lumbar disc herniation in conjunction with degenerative changes results in a medical condition often treated surgically. Besides conservative non-surgical methods such as rest, physical therapy, and bracing, often times surgical processes such as discectomy, total intervertebral disc prosthesis as well as replacement of the nucleus are now used for treatment of chronic back pain after disc herniation. ^{11,12,13,14,15,16,17} So far, no clinically established procedure is available that slows down the progression of degeneration. In this context, the question about the ability of the intervertebral disc to regenerate intervertebral disc cellular matrix subsequent to discectomy has been raised.

Repair of mild degeneration of the disc at the time of herniation, and regeneration of disc matrix following discectomy and transplantation of a variety of *in vitro* derived cell lineages has been proven in animal models. ^{18,19,20} It has similarly been shown that transplantation of similar cells into traumatic lesions of the knee, results in possible regeneration of cartilage. ^{21,22}

In the present study, regeneration of vertebral disc matrix will be assessed as an allograft transplant. Based on a proprietary technology developed at UMTB (Vivex, Inc.; Marietta, GA, USA) that retains active cells shown to offer regenerative potential and pairs them with donor-derived nucleus pulposus, a formulation has been aligned to supplement degenerative disc changes with the potential for better mechanical performance and presumably physiologic as well. The cells supporting this product are capable of differentiating into multiple lineages including disc chondrocytes given appropriate conditions and stimulating factors. ^{23,24,25}

CONFIDENTIAL	Clinical Protocol	DATE 9Dec2019	P	age
	mented Disc Regeneration in the T reatment of th or without Intervertebral Disc Herniation –	WRITER TG, DB, PW	NO. 19	REV 6

